We have a between-subjects design in which participants are randomized to one of two information conditions (independent variable). In each condition, they make a choice (dependent variable) between two hospitals (one with a non-selective donor acceptance strategy, and another with a more selective donor acceptance strategy). Independent variables: (1) Condition 1 ("baseline" condition): view only combined transplant survival (e.g. transplant survival rate not stratified by number and quality of donor hearts accepted at each center) (2) Condition 2: view only stratified transplant survival (e.g. transplant survival rate stratified into patients who received excellent donor organs and patients who received less than optimal donor organs) These two conditions will be analyzed for our primary analysis: a 1x2 design with 2 arms (control arm or combined transplant survival, and experimental arm or stratified transplant survival).

Randomization

We will use simple randomization, where each participant will be randomly assigned to one of the two predetermined conditions. The Qualtrics randomizer function will be used for randomization into a condition.

Sampling Plan

Existing Data

Registration prior to creation of data

Explanation of existing data

n/a

Data collection procedures

125 medical student participants will be recruited from University of Pittsburgh Medical School. Participants will be recruited via (1) an email to the Class of 2020, Class of 2021, and Class of 2022 listserv pages, and (2) a Facebook post on the class Facebook pages for the classes

corresponding to the listservs described. Inclusion criteria: Participants who are 2nd, 3rd, or 4th year medical students at University of Pittsburgh School of Medicine will be asked to participate if they confirm the following inclusion criteria in the consent form. (1) 18 years of age or older (2) must read and understand the information in the consent form (3) must want to participate in the research and continue with the survey (4) must live in United States Payment: Participants will be entered into a lottery for completing the survey and providing an email (the latter is optional). The lottery gives a 1 in 60 chance of winning a \$50 Amazon gift card and a 1 in 10 chance of winning a \$5 Starbucks gift card.

Sample size

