Our target sample size is 125 participants. We expect that this will amount to approximately 60 participants per condition, although due to the nature of the randomization technique used (Qualtrics randomizer function), we may end up with slightly more or slightly less than 60 per condition.

Sample size rationale

A sample size of 61 per group was calculated to yield at least 90% power to detect a 30 percentage point difference between conditions (e.g., 35% vs. 65%) with $\alpha=0.05$ (GPower 3.1.9.4).

Stopping rule

We will stop data collection after the first of the following three scenarios is achieved: (1) 125 responses collected (2) January 20, 2020 and at least 100 responses collected (3) March 31, 2020

Variables

Manipulated variables

We will manipulate how transplant center outcomes are presented. Different components of the same outcome statistics for two transplant centers will be varied over two different conditions. (1) Condition 1 ("baseline" condition): view only combined transplant survival (e.g. transplant survival rate not stratified by number and quality of donor hearts accepted at each center) (2) Condition 2: view only stratified transplant survival (e.g. transplant survival rate stratified into patients who received excellent donor organs and patients who received less than optimal donor organs) The two conditions will be included in our main analysis, which is a 2x1 design with 1 factors (transplant survival) and 2 levels per factor: "combined": reference level, in which transplant survival rate is not stratified by number and quality of donor hearts accepted at each center "stratified": transplant survival rate stratified into patients who received excellent donor organs and patients who received less than optimal donor organs

Measured variables

The outcome variable will be a binary choice between two hospitals: one with a selective donor-heart acceptance strategy and one with a non-selective donor heart acceptance strategy. Participants will respond to the question "Which Hospital do you consider to be higher performing? Please click on one of the two tables below to indicate which hospital is the better

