choice." Participants will choose between two outcome tables featuring the selective and non-selective hospital (counterbalanced, such that each of the two choices is equally likely to be presented at top of the choice scenario in each condition). The number of participants that choose each hospital will be the measured outcome variable used in analyses. On the next page of the survey, participants will respond to three mediator questions: "There are many reasons why one transplant hospital might outperform another. Which reasons were most important in your decision? Please move the slider to indicate how much you considered each of the reasons below (0=reason was not important, 100=reason was extremely important)." Participants will then move a slider bar (0-100) to indicate the importance of the following three items: (1) Patients were more likely to receive an excellent donor heart at the hospital I picked. (2) Patients were less likely to receive a marginal donor heart at the hospital I picked. (3) Patients were more likely to receive any kind of heart at the hospital I picked. The third item (more likely to receive any kind of heart) will be the only variable that is included in the planned mediation analysis.

Indices

No response

No files selected

Analysis Plan

Statistical models

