To test Hypotheses 1a /1b, we will use a binomial logistic regression analysis. The categorical independent variable will be 'stratified transplant survival'; the dependent variable is binary choice of hospital. -We will test whether the main effect of "stratified transplant survival" is statistically significant and in the predicted positive direction. To test Hypothesis 2, we will conduct a causal mediation analysis to determine whether information display had a mechanistic effect on hospital choice through our proposed mediator. We will estimate the average causal mediation effect (ACME), average direct effect (ADE), and the total effect. The ACME is the effect of the experimental information display condition (stratified) on the outcome of hospital choice (selective vs. non-selective), mediated through the hypothesized mediator (the importance of "getting any heart" at each hospital when considering the choice). The remaining effect of information display on hospital choice that is not mediated through the hypothesized mediator represents the ADE. The entire effect of the information display on hospital choice via the hypothesized mediator and the direct effect is the total effect. The proportion of the total effect that is accounted for by the ACME is called the proportion mediated.{Imai, 2010}. Analyses will be performed using the "mediation" package in R (The R Foundation for Statistical Computing).{Tingley, 2014}. We will generate 95% confidence intervals by using 1000 bootstrap simulations. The unstandardized point estimate of the ACME and its 95% confidence intervals will be interpreted. -A significant ACME for "stratified transplant survival" would suggest that stratifying transplant survival by number and quality of accepted donors works via increasing the perceived importance of "getting any heart" to increase preference for the non-selective hospital. If the ACME is non-significant, we will identify where the causal path breaks down.

No files selected

Transformations

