Logistic regression analysis: The categorical predictor "transplant survival stratified" will be dummy coded (0=not stratified, 1=stratified), with 'stratified' as the reference category. The outcome variable "choice of hospital" will be dummy-coded (0=selective hospital, 1=non-selective hospital). The reference category is 'selective hospital'. Mediation analysis: The categorical predictor "transplant survival stratified" will be dummy coded (0=not stratified, 1=stratified), with 'stratified' as the reference category. The continuous mediator variable "get any heart" will be mean-centered for each analysis. The outcome variable "choice of hospital" will be dummy-coded (0=selective hospital, 1=non-selective hospital). The reference category is 'selective hospital'.

Inference criteria

We will use the standard $p=0.05$ criteria for determining if the results are significantly different from those expected if the null hypothesis were correct.

Data exclusion

Two attention checks will be used. The data will be analyzed with all participants, and with only the participants who pass both of these attention checks.

Missing data

If a participant does not complete the entire survey, they will not be included in the analysis.

Exploratory analysis

No response

Other

Other

No response

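### The mediated effect in H2 is open to confounding: only the display is randomised, and the plan lists no covariate and no sensitivity analysis for the rating-to-choice path

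*Combined protocol and SAP*

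**What the plan says.** - **What is randomised.** Design Plan, Randomization: "We will use simple randomization, where each participant will be randomly assigned to one of the two predetermined conditions". This allocates the display and nothing else.
- **Who is sampled.** Data collection procedures: "Participants who are 2nd, 3rd, or 4th year medical students at University of Pittsburgh School of Medicine". Class year serves as an eligibility condition and a recruitment route. No analysis uses it.
- **What is measured.** Measured variables lists the hospital choice, then three importance sliders on the following page. On the mediator it says: "The third item (more likely to receive any kind of heart) will be the only variable that is included in the planned mediation analysis". In context this picks one slider out of three, so it does not by itself exclude covariates. However, Statistical models and Transformations name only condition, rating and choice.
- **What is claimed.** Statistical models: "we will conduct a causal mediation analysis to determine whether information display had a mechanistic effect on hospital choice through our proposed mediator". The ACME, direct effect, total effect and proportion mediated are to be estimated with 1000 bootstrap simulations. A significant ACME would be taken to suggest that stratification acts by raising the importance of getting any heart.
- **What is absent.** No assumption about shared causes of rating and choice is stated, and no sensitivity analysis for them is planned. Exploratory analysis has no entry.

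**The concern.** The ACME joins two paths. The display-to-rating path is protected by randomisation. The rating-to-choice path is not, because students are not assigned to rate 'any heart' high or low. Suppose a student arrives already concerned about donor shortage. That student may rate the item highly and also favour the accepting hospital, for reasons unrelated to the rating itself. The fitted rating-to-choice slope then absorbs the background association, and the ACME inherits it. Bootstrapping measures sampling error and leaves this bias in place.

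At stake is the mechanistic conclusion of a stated hypothesis: a significant ACME could appear with no mediation at all.

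**Working it through.** **1. The plan's own figure.** The only design calculation is for H1: "A sample size of 61 per group was calculated to yield at least 90% power to detect a 30 percentage point difference between conditions", with 35% vs 65% as the example and α = 0.05. Enumerating Fisher's exact test (two-sided) at 61 per group gives 90.07% power, so the figure reproduces. It says nothing about mediation.

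**2. Inputs.** From the documents: N = 125 (Sample size), allocation about 1:1, choice rates 0.35 and 0.65. Assumed, because the documents give no figures: the display raises the rating by 0.8 SD; a binary background factor U has prevalence π, shifts the rating by g_m SD and shifts choice by g_y log-odds. The true effect of rating on choice is zero.

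**3. Model.**
- M = 0.8T + g_m(U − π) + N(0,1)
- logit P(Y=1) = −0.62 + 1.24T + g_y(U − π)
- With g_y = 0, the choice rates are 1/(1+e^0.62) = 0.35 and 1/(1+e^−0.62) = 0.65.

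**4. Approximate bias by hand.** If U is left out, the spurious rating-to-choice slope is about

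g_y × g_m π(1−π) / [1 + g_m² π(1−π)].

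Multiplying by 0.8 (display to rating) and by p(1−p) = 0.35 × 0.65 = 0.2275 gives the spurious ACME. Moderate case (g_m = 0.8, g_y = 1.1, π = 0.5):
- 0.8 × 0.25 / (1 + 0.64 × 0.25) = 0.2/1.16 = 0.172
- 0.172 × 1.1 = 0.190; × 0.8 = 0.152; × 0.2275 = 0.035, or about 3.5 percentage points.

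**5. Simulation.** n = 125, linear mediator model, logistic outcome model, 95% simulation intervals for the ACME. Ranges are across repeated runs; with 600 trials per run, the Monte Carlo standard error at 19% is √(0.19 × 0.81/600) = 1.6 points.

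| Assumed U | Hand ACME (points) | Simulated ACME (points) | Significantly positive, unadjusted | Adjusted for U |
|---|---|---|---|---|
| None | 0 | about 0 | 2–3% | 2–3% |
| Weak: 0.5 SD, 0.7 log-odds, π = 0.5 | 1.5 | 1.6 | 5–7% | 2–3% |
| Moderate: 0.8 SD, 1.1, π = 0.5 | 3.5 | 3.4–3.8 | 17–20% | 2–3% |
| Strong: 1.0 SD, 1.4, π = 0.5 | 5.1 | 4.9 | 32–37% | 2–4% |
| Moderate, π = 0.2 | 2.3 | 2.6 | 11% | 3% |
| Moderate, π = 0.1 | 1.4 | 1.3 | 5–6% | 2–3% |
| Moderate, π = 0.5, U acts on choice in condition 2 only | – | 1.7–2.1 | 5–10% | 2–3% |

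The nominal rate in the upper tail is 2.5%.

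**6. A second set-up.** Rating SD 25, display effect 12.5 points, a continuous U, N = 122, and a joint-significance test in place of the bootstrap. U's correlation with the rating was 0.3 or 0.5, and its effect on choice 0.5 or 1.0 log-odds per SD. The spurious ACME ran from 0.016 to 0.050 (5–17% 'mediated'). False-positive mediation was 9–45% unadjusted against 3–5% adjusted, and 4.0% with no shared cause.

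**7. What adjustment cannot reach.** The rating follows the choice and asks about the hospital already chosen. With no shared cause and no effect of rating on choice, let the choice itself raise the rating by 5, 10 or 20 points (SD 25). The ACME is then 0.003, 0.010 or 0.040, and adjusting for a background covariate leaves each value unchanged.

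**The case against.** A reader might infer that the mediation estimate *is* confounded. The documents do not show this: nothing in them demonstrates that training stage or transplant exposure shifts either the rating or the choice. Several further points count against a stronger claim.

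- **Not recorded?** Measured variables need not be the whole questionnaire; the two attention checks under Data exclusion are not in it either. Class year may be known from the eligibility check. Only 'not listed and not planned for use' is supported.
- **Common introduction.** Every participant is introduced to the donor match process before the table (Description). That may narrow differences in prior knowledge, by an unknown amount.
- **Condition 1.** As described, the combined table may not reveal which hospital accepts more hearts, so a prior preference could be hard to express there. Restricting the effect to condition 2 lowers the moderate case to about 5–10%.
- **Prevalence.** A 50/50 split may suit class year but not prior transplant exposure, which could be much rarer.
- **Does the ACME alone settle H2?** No. H2 also predicts that ratings differ by condition, which is a randomised contrast.
- **Best case.** The adjusted column conditions on the exact shared cause. Class year and a self-reported exposure item would be proxies.

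These points limit the size and certainty of the problem. They do not supply a covariate, a stated assumption or a sensitivity analysis, and the rating-to-choice path remains unprotected.

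**Conclusion.** The point holds as a gap in identification. The ACME, direct effect and proportion mediated have a causal reading only if rating and choice share no unmeasured cause; the plan neither states nor probes that assumption. H1, the total effect, the comparison of ratings by condition and the stated sample size are untouched.

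The size cannot be derived from the documents. Depending on the assumed strength, prevalence and site of action of the background factor, the chance of a falsely positive ACME runs from barely above nominal (about 5%) to about 37% in the main set-up. The change is worth making because a stated hypothesis depends on it and the remedy is cheap. It does not threaten the primary comparison.

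**What to change.** 1. **Sensitivity analysis, first priority.** Pre-specify how the ACME varies over a range of residual mediator–outcome correlation, with a probit outcome model so that this correlation is defined. Report the value at which the ACME loses its sign or its significance.
2. **Covariates.** Before the display, record class year and one yes/no item on prior transplant exposure (rotation, research or family). Enter both in the mediator model and the outcome model.
3. **Wording.** Report a significant ACME as consistent with mediation under an assumption of no unmeasured confounding. State that neither step above deals with the rating being taken after the choice and about the hospital already chosen.

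Cost: two short questions, a few lines of code, and possibly a slightly wider ACME interval if the covariates predict little. If collection is already complete (the latest date in the stopping rule is March 31, 2020), items 1 and 3 need no new data, and class year can still be used if it was kept.

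### The whole-survey completion rule drops participants from the H1 test even though their condition and hospital choice are already recorded

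*Combined protocol and SAP*

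**What the plan says.** The Missing data section states: "If a participant does not complete the entire survey, they will not be included in the analysis". It makes no distinction between H1 (effect of condition on choice) and H2 (mediation).

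Under Statistical models, H1 is a logistic regression with condition as the only predictor, and "the dependent variable is binary choice of hospital". Under Measured variables, the choice comes first: "On the next page of the survey, participants will respond to three mediator questions". Of those three sliders, the third (any kind of heart) "will be the only variable that is included in the planned mediation analysis".

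The Stopping rule ends collection at the first of three events. The first two are given as "1) 125 responses collected (2) January 20, 2020 and at least 100 responses collected"; the third is 31 March 2020. The plan does not say whether a response means a completed survey. Under Data collection procedures, "Participants will be entered into a lottery for completing the survey".

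The Data exclusion section adds: "The data will be analyzed with all participants, and with only the participants who pass both of these attention checks". It does not say which of the two results decides.

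**The concern.** Leaving the survey after the choice page happens after both randomisation and the H1 outcome. Excluding those participants selects the H1 sample on an event that could depend on both. Two things are at stake:

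- **Precision.** Recorded primary outcomes are thrown away, and the sample has little slack: 125 in total against a requirement of 61 per group, or 122.
- **Protection against bias.** "each participant will be randomly assigned to one of the two predetermined conditions", but a comparison of completers is no longer fully protected by that randomisation.

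H2 does need the third slider, and H1 does not. As written, even a participant who gave the third rating is lost to both analyses if anything else in the survey is unfinished.

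**Working it through.** **Inputs from the plan.** 35% vs 65%, α = 0.05, 61 per group for at least 90% power (Sample size rationale); 125 participants (Sample size); a possible stop at 100 responses (Stopping rule); simple randomisation to two conditions (Randomization).

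**Assumed.** A two-sided test, since sidedness is not stated; all drop-off rates.

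**Step 1: reproduce the plan's figure.** Exact enumeration of the two-sided Fisher test gives power 0.901 at 61 per arm and 0.892 at 60, so 61 reproduces. The Wald formula for the log odds ratio agrees:

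- n = (z₀.₉₇₅ + z₀.₉₀)² × [1/(p₁(1−p₁)) + 1/(p₂(1−p₂))] / (log OR)²
- log OR = ln[(0.65/0.35)/(0.35/0.65)] = 1.238
- variance term = 2/0.2275 = 8.791
- n = (1.960 + 1.282)² × 8.791 / 1.238² = 60.3, rounded up to 61

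**Step 2: power after loss.** If d is the fraction leaving after the choice, the rule keeps N(1−d) for H1, whereas using recorded choices keeps N. Wald power is by exact binomial enumeration averaged over simple 1:1 randomisation. Fisher power is with equal arms.

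| Responses | Loss | Analysed | Wald power | Fisher power (per arm) |
|---|---|---|---|---|
| 125 | 0% | 125 | 92.5% | 90.8% (62) |
| 125 | 5% | 119 | 90.8% | 88.4% (59) |
| 125 | 10% | 112 | 89.3% | 85.3% (56) |
| 100 | 0% | 100 | 86.1% | 82.8% (50) |
| 100 | 10% | 90 | 81.5% | 75.0% (45) |

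A 10% loss from 125 is 112.5. Rounding up to 113 gives Wald 89.8%.

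**Step 3: when the rule biases H1.** Let p be the true proportion choosing the non-selective hospital, and let r_non and r_sel be the fractions of non-selective and selective choosers who finish. Among completers:

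- observed proportion = p·r_non / [p·r_non + (1−p)·r_sel]
- observed odds = true odds × r_non/r_sel

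The odds ratio is distorted only if r_non/r_sel differs between conditions. If drop-off depends on condition only, the ratio is 1 in each arm. If it depends on choice only, the ratio is the same in both arms and cancels. With no true effect, the odds ratio stays 1.00 in either case.

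Assumed example with no true effect (50% in both conditions):

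- Condition 1: 10% leave whatever they chose, so completers show 50.0%.
- Condition 2: 15% of selective and 5% of non-selective choosers leave, so completers show 0.5×0.95/(0.5×0.95 + 0.5×0.85) = 0.475/0.900 = 52.8%.
- Spurious odds ratio = 0.95/0.85 = 1.12.
- With 56 completers per arm, Wald rejection in the predicted direction is 4.5%, against 2.3% under uniform 10% drop-off. Two-sided rejection goes from 4.7% to 5.6%.

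**Step 4: the two attention-check sets (secondary).** Suppose success in either set could be claimed, which the plan does not say. Treat the two test statistics as bivariate normal with correlation √(1−f), where f is the assumed check-failure rate. A false claim in the predicted direction then rises from 2.5% to 3.0% at f = 5% and 4.2% at f = 50%. H1 requires the predicted direction, so no excess over 5% is shown.

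**The case against.** **No harm is demonstrated.** The plan gives no drop-off rate, and the lottery rewards completion. On the planned logistic test, a 5% loss still leaves 90.8% power; the larger drops come from Fisher's test, which is not the planned analysis. If a response means a completed survey, losses are replaced up to the target. The 86.1% at 100 responses comes from the stopping rule, and only the further fall to 81.5% belongs to this rule. All of this stands, and it limits the size of the concern. Replacement restores numbers, however, and does not undo selection after the outcome.

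**The bias pattern is constructed.** The slider items are the same in both conditions, nothing in the plan points to joint dependence on condition and choice, and two-sided rejection in the example moves only from 4.7% to 5.6%. This stands as a statement about likelihood. The pattern remains possible, because the next page asks people to weigh reasons for the hospital they have just picked.

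**The rule is prespecified, applies equally to both conditions, and keeps H1 and H2 on one sample.** True, but equal application does not prevent selection that differs by condition, and slightly different samples for H1 and H2 are easily reported.

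**Partial records could admit repeat entries.** Recruitment is by email and Facebook, giving an email address is optional, and no check for duplicates is described. Someone who abandons and restarts could be counted twice. This is an inference, but a fair one. It calls for a sentence on duplicates and does not justify discarding recorded choices.

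**The plan already analyses all participants.** That wording contrasts everyone with those who pass the attention checks. It does not clearly restore non-completers, whom the next section removes.

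**Conclusion.** The concern holds. The completion rule covers H1 and excludes participants who have both H1 variables recorded, and the plan gives no reason for this.

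The size of the effect is unknown. With 125 responses, an assumed 10% unreplaced loss costs about 3 points of Wald power (92.5% to 89.3%); with 100 responses it costs about 5 points (86.1% to 81.5%). If responses means completed surveys, there is no such loss under the numerical targets. Bias arises only if drop-off depends jointly on condition and choice; neither effect is shown to occur.

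The change is worth making because it removes any bias from drop-off after the choice, keeps recorded data and costs almost nothing. It cannot recover participants who leave after randomisation but before choosing. The unstated deciding set and the undefined meaning of responses are secondary, and the conclusion does not rest on them.

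**What to change.** Amend the Missing data and Data exclusion sections as follows:

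- **H1:** include every randomised participant with a recorded hospital choice, by assigned condition, whether or not later pages were completed.
- **H2:** additionally require a recorded any-kind-of-heart rating, and no other later item.
- **Analysis sets:** name the all-participants set as primary and the attention-check subset as a sensitivity analysis.
- **Stopping rule:** say whether responses means completed surveys.
- **Reporting:** give, by condition, the numbers who left before choosing, left after choosing, or were excluded for any other reason.
- **Repeat entries:** state how they are identified and handled, since partial records will now count.

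The cost is a few sentences and no extra data. The H1 and H2 samples may differ by a few participants, which should be reported.
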